## 9.7.3 Interim Analysis

No interim analysis was planned.

## 9.7.3.1 Data Safety Monitoring Board

No Data Safety Monitoring Board was planned for this non-randomized, unblinded study.

#### 9.7.4 Other Statistical and Analytical Issues

## 9.7.4.1 Handling of Missing Data

In order to assess sensitivity of results due to missing data, two types of analyses were to be performed: last observation carried forward (LOCF) and observed case (OC). The primary data set for efficacy analyses by visit was to be the LOCF data set derived from the Phase B efficacy sample. The LOCF data set would have included data recorded at a scheduled Phase B visit or, if no observation was recorded at that visit, data carried forward from the previous scheduled Phase

Final; 26 Feb 2018 Page 57 of 80

B time point. Baseline data (i.e., Day 0 in Phase B) were not to be carried forward to impute missing values for the LOCF data set. Analyses based on the OC data set were to be performed. The OC data set would have consisted of the actual observations or hospitalization/ED data recorded at each relevant time point.

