The treating clinician performed a clinical interview and mental status examination based on current clinical standards of care at all outpatient visits, whether scheduled or unscheduled. All episodes of clinical care (i.e., psychiatric and non-psychiatric) were recorded in the source documentation. In addition, the following clinical evaluations were performed as outlined in Table 3:

- Routine vital signs (e.g., blood pressure, heart rate, respiratory rate, and temperature) at each visit
- Height, weight and calculation of BMI at each visit
- Fasting lipid tests [e.g., fasting triglycerides, cholesterol (total, HDL, LDL)]
- HbA1c
- Additional clinical laboratory testing (e.g., hematology, fasting clinical chemistry, prolactin, urinalysis and urine pregnancy test) as described in Table 3 and clinically indicated and determined by treatment team
- AEs and concomitant medications
- CGI-I
- PSP
- C-SSRS (Since Last Visit) for suicidality
- AIMS, BARS, and SAS to assess EPS
- Injection site reaction (i.e., localized pain, redness, swelling, and induration)

Final; 26 Feb 2018 Page 29 of 80

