#### **DOCUMENTATION OF PREVIOUS HOSPITALIZATIONS**

Data regarding psychiatric and non-psychiatric hospitalizations and medical interventions occurring within the 6 months prior to the date of the signing the ICF were obtained by searching MO HealthNet (Medicaid) and the DMH database or confirmed through all available medical records and reliable data from caregivers.

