#### 9.5.1.5 Adverse Events and Other Events of Interest

An AE is any untoward medical occurrence in a subject or clinical investigation subject administered a drug under study. An AE does not necessarily have a causal relationship with the study drug. For this study, the study drug was aripiprazole once monthly and oral aripiprazole.

The criteria for identifying AEs were:

- Any unfavorable and unintended sign (including an abnormal laboratory finding), symptom, or disease temporally associated with the use of a drug under study, whether or not considered related to the drug under study
- Any new disease or exacerbation of an existing disease

Final; 26 Feb 2018 Page 40 of 80

LDL = low-density lipoprotein

a: Triglycerides were measured at screening only, to rule out exclusionary values

b: Serum β-hCG was performed if the subject or investigator suspected that the subject may be pregnant

- Any deterioration in nonprotocol-required measurements of a laboratory value or other clinical test (e.g., ECG or x-ray) that results in symptoms, a change in treatment, or discontinuation of study drug
- Recurrence of an intermittent medical condition (e.g., headache) not present pretreatment (i.e., baseline)
- An abnormal laboratory test result was considered an AE if the identified laboratory abnormality led to any type of intervention, whether prescribed in the protocol or not.

A laboratory result was to be considered by the investigator to be an AE if it:

- Resulted in the withdrawal of study drug
- Resulted in withholding of study drug pending some investigational outcome
- Resulted in an intervention, based on medical evaluation (e.g., potassium supplement for hypokalemia)
- Resulted in any out of range laboratory value that in the investigator's judgment fulfills the definitions of an AE with regard to the subject's medical profile

All AEs observed during the study were reported on the CRF. All AEs, regardless of relationship to study drug or procedure, were collected beginning from the time the subject signed the study ICF through the last visit. Serious AEs were collected for 30 days after the last dose or at the Follow-up Visit, whichever came later.

Abnormal laboratory values were not listed as separate AEs if they were considered to be part of the clinical syndrome that is being reported as an AE. Any laboratory abnormality considered to constitute an AE was reported as an AE on the CRF.

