d: Previous medications taken within 7 days prior to starting study drug and all central nervous system-active compounds taken within 30 days preceding the first dose of study drug were recorded. All antipsychotic medications used within 6 months of screening were recorded.

e: A urine pregnancy test was performed for women of childbearing potential only at screening, Visit 10, and at the Follow-up visit; subsequent testing was done as is clinically indicated. If a subject or investigator suspected that the subject may be pregnant, a serum pregnancy test would then be performed.

**Table 3:** Schedule of Assessments

Visit				2	3	4	5	6	7	8 q
Study Period	Screening/ Assessment	Phase A (Oral Tolerability Phase a )			Pha	nse B (Trea	tment Ph	ase)		
Day	Variable	-3 to -1	Baseline Day 1 b,g	15 g	30	60	90	120	150	180
Week				2 e	4	8	12	16	20	24
Procedure										

- f: Data regarding psychiatric and non-psychiatric hospitalizations and medical interventions occurring within the 6 months prior to the date of the signing the ICF were obtained by searching MO HealthNet (Medicaid) and MO Department of Mental Health (DMH) data via collaboration with the Missouri Institute of Mental Health (MIMH); availability of Medicaid data and documentation of at least one inpatient hospitalization or ED visit within the previous 6 months was required for eligibility.
- g: For subjects who were psychiatrically stabilized and discharged prior to the completion of the required 14-day course of oral aripiprazole, a pre-discharge assignment was given to a CSW or SC. The CSW/SC maintained regular contact with the subject until the Week 2 visit. Following the Week 2 visit, subjects had contact with their assigned CSW/SC based on routine clinical care.
- h: At all outpatient visits, scheduled or unscheduled.
- i: Vital signs were recorded daily while hospitalized.
- j: BMI was calculated as: mass (kg)/height (m2).
- k: Subjects should have been fasting for a minimum of 10 hours prior to blood draws for all laboratory assessments. Every effort was made to obtain the clinical laboratory samples at the same time of day at each visit. All laboratory testing was performed at local laboratories at the clinical sites.

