## 9.5.5 Completion/Discontinuation of Subjects

A subject could elect to discontinue the study at any time for any reason without prejudice. All subjects who discontinued the study were to complete the study's early discontinuation procedures indicated in the Schedule of Assessments (Table 3) whenever possible.

The investigator promptly explained to the subject involved that the study would be discontinued for that subject and provided appropriate medical treatment and other necessary measures for the subject. A subject who ceased to return for visits was followed up by mail, phone, or other means to gather information such as the reason for failure to return, the status of treatment compliance, the presence or absence of AEs, and clinical courses of signs and symptoms. This information was recorded in the CRF.

Subjects who discontinued early from the study were discontinued for one of these primary reasons: AE(s), lost to follow-up, subject choice, inadequate therapeutic effect, withdrawal of consent, pregnancy, study termination, or other (to be specified). In addition to the primary reason, the subject could indicate one or more secondary reasons for discontinuation.

A subject removed from the study for any reason could not be replaced.

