## 9.5.6 Confirmation of Medical Care by Another Physician

The investigator instructed subjects to inform site personnel when they were planning to receive medical care by another physician. At each visit, the investigator asked the subject whether he or she had received medical care by another physician since the last visit or was planning to do so in the future. When the subject was going to receive medical care by another physician, the investigator, with the consent of the subject, informed the other physician that the subject was participating in the clinical study.

Final; 26 Feb 2018 Page 51 of 80

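### Admissions before consent are searched for in Medicaid/DMH data, but no such search is planned for the 180 days after discharge, so later admissions of subjects who leave can be missed

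*Combined protocol and SAP*

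**What the plan says.** **Before treatment.** Section 9.5.1.3 obtains prior admissions by "searching MO HealthNet (Medicaid) and the DMH database or confirmed through all available medical records and reliable data from caregivers". Footnote f of Table 3 fixes the window: "Data regarding psychiatric and non-psychiatric hospitalizations and medical interventions occurring within the 6 months prior to the date of the signing the ICF". Section 9.1.2 describes the same search and the same 6 months, and Table 3 marks hospitalization documentation at Screening only.

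**After discharge, while the subject attends.** Section 9.1.4.2 states "All episodes of clinical care (i.e., psychiatric and non-psychiatric) were recorded in the source documentation". Section 9.5.6 adds "At each visit, the investigator asked the subject whether he or she had received medical care by another physician since the last visit".

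**After the subject leaves.** Three provisions remain:
- Section 9.5.1.5: "Serious AEs were collected for 30 days after the last dose or at the Follow-up Visit, whichever came later". Inpatient admission counts as an SAE under Section 9.5.1.6.
- Section 9.1.4.3: one safety call about 30 days after the last visit, unless consent is withdrawn.
- Section 9.5.5: "A subject who ceased to return for visits was followed up by mail, phone, or other means to gather information such as" the reason for not returning, compliance, AEs and clinical course. It has no hospitalization item and no end date.

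**Analysis.** The core efficacy set is everyone entering Phase B, though Section 9.7.1.4 allows other datasets derived from it. Section 9.7.4.1 says "The primary data set for efficacy analyses by visit was to be the LOCF data set derived from the Phase B efficacy sample", and of the second data set, "The OC data set would have consisted of the actual observations or hospitalization/ED data recorded at each relevant time point". Section 9.7.1.9 plans repeated measures ANCOVA. Kaplan-Meier appears only for time to discontinuation (Section 9.7.1.10). Section 9.3 expects 40% drop-out.

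**The concern.** Each subject is his or her own control, so no concurrent arm absorbs a difference in how admissions are found. An admission on day 150 in a subject who left on day 60 lies outside every time-limited provision. The corresponding admission before consent would be found by the search. Missed post-period admissions then look like drug benefit.

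At stake are the 180-day re-hospitalization rate, which is one of the three primary outcome models in Section 9.7.1.9, and the number of stays and total hospital days (Sections 9.7.1.2 and 9.7.1.10). Section 9.2 nevertheless presents the windows as roughly equivalent.

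**Working it through.** **Drop-out inputs.** The plan's 177 reproduces as 90 × 1.4 × 1.4 = 176.4. That inflation implies attrition of 1 − 1/1.4 = 28.6%, not the stated 40%, so both values are used.

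**Assumptions, none fixed by the documents.**
- 180-day risk is 30% in both periods. This is the pre-switch figure in Section 9.7.2, which has no stated window.
- The index admission is not counted.
- The admission hazard is constant.
- Exit is uniform over 180 days and unrelated to admission.
- Capture continues for c = 30 days after exit.
- Leavers are kept, and any-event status is cumulative.

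**Formula.** λ = −ln(0.7)/180 = 0.001982 per day. With drop-out d and horizon T:

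observed = (1 − d)(1 − e^(−λT)) + d × mean over u ~ U(0,180) of [1 − e^(−λ·min(T, u+c))]

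**180 days.** The captured risk in leavers is 1 − [(e^(−30λ) − 0.7)/λ + 30 × 0.7]/180 = 0.204.
- d = 0.40: 0.60 × 0.300 + 0.40 × 0.204 = 0.2616, a relative shortfall of 13%.
- d = 0.286: 0.714 × 0.300 + 0.286 × 0.204 = 0.2726, a shortfall of 9%.
- With no capture after exit (c = 0), the figures are 0.2436 (19%) and 0.2597 (13%). For exit unrelated to admission, these are upper bounds.

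**90 days.** The true risk is 0.1633. Observed is 0.1564 (4%) at d = 0.40 and 0.1584 (3%) at d = 0.286.

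**30 days.** Nil, because u + 30 is never below 30. With c = 0 the shortfall is 3% or 2%.

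**Base risk.** From 15% to 50%, the 180-day shortfall runs from 13% to 12% (d = 0.40) and from 10% to 8% (d = 0.286).

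**Person-days.** Leavers contribute [150 × (30 + 180)/2 + 30 × 180]/180 = 117.5 days on average. The overall mean is 0.60 × 180 + 0.40 × 117.5 = 155, or 162 at d = 0.286. Expected stays therefore fall short by 14% or 10%.

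**If some exits follow a recorded admission** (d = 0.40, overall risk held at 30%):
- A quarter of exits: 0.10 of subjects are already counted, and the risk in the rest is 0.20/0.90 = 0.222. The same formula gives about 0.28 overall, a shortfall of 7%.
- Half of exits: the risk in the rest is 0.10/0.80 = 0.125. Observed is about 0.292, a shortfall of 3%.

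If exit tends to come before an unseen relapse, the shortfall exceeds 13%.

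**Test size.** This applies only if the index admission is not counted. In simulation, a two-sided 5% paired test at 180 days with no true effect rejects in about 9% of trials (106 entrants = 177 × 0.6, d = 0.40) or 8% (126 = 177/1.4, d = 0.286). Full capture gives 5%. Note that 106 entrants at 40% drop-out leave about 64 completers, not 90. Reaching 90 needs 90/0.6 = 150 entrants, and the rate is then about 11%.

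**The case against.** A reader might infer that the 180-day result would necessarily favour the drug. The documents do not support that. No section specifies cumulative coding. The LOCF sentence is confined to analyses by visit, and a fixed-window admission rate is not clearly one of these. The only sentence in Section 9.7.4.1 that names hospitalization data describes observed cases. Carrying interval values forward has no fixed direction. Under one reading of observed cases, leavers drop out of the analysis, and the problem becomes selection of those who stay. The LOCF column of Table 8 does list ER visits and hospitalizations, but these come from one subject and do not settle the coding rule. All of this stands, so the direction is conditional.

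The primary endpoint wording in Section 9.7.1.1 can be read as on-treatment, which would put later admissions out of scope. That also stands as a reading, but a rule for exposure or denominator would still be missing.

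The pre-period search is not guaranteed either. Records and caregivers are an alternative, and Medicaid-eligible subjects may enter. Incomplete pre-period data would work the other way, by an amount the documents do not give. Using one method for both periods deals with both errors.

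A reader might also take the rejection rates as describing the written plan. They do not. Sections 9.7.1.9 and 9.7.2 count the index admission, so the pre-period rate is 100% and a 180-day any-event test rejects whatever the capture. That is a separate and larger problem.

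**Conclusion.** The unequal capture is real. The claims search is tied to the period before consent, and nothing specified secures admission data to day 180 for early leavers. The analysis neither adjusts for unobserved time nor says how an admission outcome is derived for them.

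If leavers are kept and outcomes are cumulative, the 180-day any-event rate is understated by roughly 9 to 13% in relative terms. Expected stays fall short by 10 to 14%, and hospital days are understated in the same direction. The any-event shortfall at 40% drop-out is 3 to 7% if many exits follow a recorded admission, and more than 13% if exit precedes relapse. The shortfall in the post-period estimate arises whether or not the index admission is counted.

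This does not undermine the named 30-day primary comparison, where the computed effect is nil. It is also not an error in a result, because Section 9.7 records that no formal analysis was performed. It is a gap in the plan that should be fixed.

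**What to change.** For every Phase B subject, regardless of withdrawal and subject to consent, apply the pre-period method to the 180 days after index discharge: the same Medicaid/DMH search, with records where claims are unavailable. Add this to Section 9.5.1.3 and Table 3.

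In Section 9.7, state that:
- the hospitalization, ED and hospital-day outcomes follow the ITT set, which settles the on-treatment reading of Section 9.7.1.1;
- LOCF is not used for them;
- where coverage ends early, follow-up is censored (Kaplan-Meier), or a count model is used with log person-days as offset.

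The look-up is the main remedy. When exit is unrelated to admission, simulation shows that both analysis methods work: the mean Kaplan-Meier 180-day estimate is 0.300 to 0.302 against a true 0.300, and the person-day comparison of stays rejects one-sided in 2.2 to 2.6% of trials against 2.5%. Neither is enough if exit is related to relapse.

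The cost is one more data pull through the existing claims collaboration, some claims lag, SAP wording, and possibly consent wording for look-up after withdrawal (the consent pages were not available for review). The post-period rate may also look less favourable.

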#### 9.8 CHANGE TO THE CONDUCT OF THE STUDY OR ANALYSES

#### 9.8.1 Protocol Amendments

There were three amendments to the protocol; major changes are described below.

## 9.8.1.1 Amendment 1.0, 17 Dec 2015

- Study population recruitment procedures and locations were clarified.
- Updated text to reflect the change in the product labeling that allows for deltoid injections and the reason for administration of oral aripiprazole was added for consistency.
- Pre-Screening assessments to help investigators identify any subjects with literacy or capacity to consent issues prior to study enrollment were added.
- The Follow up Period was eliminated from the study duration.
- Study population recruitment procedures and locations were clarified.
- The IRB requirement regarding consent by a legal representative in addition to the subject as part of the inclusion criteria was eliminated.
- Corrected text to clarify the accountability documentation to OAPI, including the elimination of the need for FDA Form 1572.
- Removed waiting time requirement after IM injection during injection site evaluation.
- Study duration was changed, resulting in elimination of Visit 9.
- Added text regarding the time period for the collection of safety information and the definition of safety information.
- Moved text regarding safety endpoints into a new section as they are considered exploratory endpoints.

#### 9.8.1.2 Amendment 2.0, 26 Feb 2016

- Added text to clarify use of olanzapine and aripiprazole during study duration; text added to
  clarify the type of antipsychotic allowed during Screening Period; added text to describe
  decision procedures for aripiprazole once monthly injection administration; added text
  regarding long-acting antipsychotics as exclusionary medications with the exception of
  aripiprazole once monthly.
- Added text regarding how data regarding psychiatric and non-psychiatric hospitalizations will be confirmed; text regarding timing of hospitalization and types of documentation to determine eligibility was added for clarification; added text to clarify that DSM-5 diagnosis of schizophrenia must be current.
- Added text regarding aripiprazole dosage decrease.
- Updated inclusion and exclusion criteria.
- Score cap for the UBACC was removed to allow for greater flexibility for inclusion on the study.

Final; 26 Feb 2018 Page 58 of 80

- Updated text to clarify that the diagnosis of schizophrenia according to DSM-5 criteria had to be current; added text describing methods for confirmation of data regarding psychiatric and non-psychiatric hospitalizations and medical interventions.
- The primary efficacy endpoint was reworded for clarity and consistency with other sections (administrative change).

#### 9.8.1.3 Amendment 2.1, 24 Aug 2016

- Added text to clarify when screening for eligibility for entry into the study will occur.
- Added text to clarify that olanzapine is no longer considered an exclusionary medication during the Screening Period, except for those who are eligible for Phase A.
- Added text to clarify the use of long-acting injectable aripiprazole during Phase B for all subjects and eligibility of subjects who were clinically started on long-acting injectable aripiprazole during hospitalization just prior to study entry.
- Updated text to clarify timing and use of baseline assessments for determining tolerability to oral aripiprazole during Phase A of the study; removed text to clarify timing of Phase B baseline/Day 1.
- Added text regarding timing of the collection of baseline data during Phase B for subjects that are enrolled after starting long-acting injectable aripiprazole in the hospital.
- Added text stating that the Study Coordinator can receive a pre-discharge assignment, in addition to a community support worker, for subjects who are psychiatrically stabilized and discharged prior to the completion of the required 14-day course of oral aripiprazole.
- Added text to clarify which clinical laboratory tests require fasting according to when they are performed (i.e., Screening Period versus Baseline Visit)
- Added text regarding the eligibility of subjects already clinically started on long-acting injectable aripiprazole during the hospitalization just prior to study entry.
- Added text regarding the timing of the Baseline Visit and how baseline assessments are to be conducted.
- Updated text regarding how and which baseline assessments will be conducted.
- Updated exclusion criteria.

Final; 26 Feb 2018 Page 59 of 80

## 11 EFFICACY

This study was terminated due to lack of enrollment. An insufficient number of subjects were enrolled to analyze the data for efficacy. Efficacy data collected are provided in Appendix 2Appendix 1.

Final; 26 Feb 2018 Page 61 of 80

#### 12 SAFETY

#### 12.1 BASELINE ASSESSMENTS AND SCREENING

Baseline and screening data collected are provided in Table 5 and Appendix 2.

**Table 5:** Baseline and Screening Assessments

	Result
Baseline Data Category	N = 8
Age, mean (SD)	32.84 (8.69)
Gender, n (%)	8 (100.0)
Male	3 (37.50)
Female	5 (62.50)
Race, n (%)	8 (100.0)
Caucasian	2 (25.00)
Black	6 (75.00)
Ethnicity, n (%)	8 (100.0)
Hispanic	0 (0.00)
Not Hispanic	8 (100.00)
CGI, Severity of Illness, n (%)	8 (100.0)
Moderately Ill	1 (12.50)
Markedly Ill	5 (62.50)
Severely Ill	2 (25.00)
BMI (kg/m  ), mean (SD)	29.08 (7.88)
Height (cm), mean (SD)	167.48 (13.40)
Weight (kg), mean (SD)	80.02 (16.36)
Fasting Lipids (mg/dL), mean (SD)	
Total Cholesterol	169.75 (32.38)
Triglycerides	97.63 (58.34)
HDL cholesterol	66.25 (33.97)
LDL choloesterol	84.13 (28.38)
HbA1c (%), mean (SD)  RMI = body mass index CGI = Clinical Global Impression. Hb	5.11 (0.28)

BMI = body mass index, CGI = Clinical Global Impression, HbA1c = glycosylated hemoglobin, HDL = high-density lipoprotein, LDL = low-density lipoprotein, SD = standard deviation

